17.2	Participant Discontinuation/Withdrawal from the Study	17
17.3	Early Termination Study Visit	Error! Bookmark not defined.
18.	RECORDINGS.....	18
19.	IRB REVIEW HISTORY	18
20.	COORDINATING CENTER for MULTI-Site Studies	18
20.1	Participating Sites	18
20.2	Description of Collecting Sites.....	18
20.3	Study-Wide Number of Participants.....	18
20.4	Communication to Participating Sites	18
21.	REFERENCES / BIBLIOGRAPHY	18

A Pragmatic Randomized Clinical Trial Comparing Rectilinear Biphasic Waveform and Biphasic Truncated Exponential Waveform Shocks for Cardioversion of Atrial Fibrillation (Zoll vs Lifepak-RCT) |

PI: [name]

A Pragmatic Randomized Clinical Trial Comparing Rectilinear Biphasic Waveform and Biphasic Truncated Exponential Waveform Shocks for Cardioversion of Atrial Fibrillation (Zoll vs Lifepak-RCT) |

PI: [name]

Study Phase	Screening (Pre-Op)	Treatment/Intervention (EP Lab or CDU Procedure Suite)
Informed Consent/Assent	X	
Review Inclusion/Exclusion Criteria	X	
Duration of AF Assessment (< 7 days, 7 days-365 days, > 365 days)	X	
Months since AF diagnosis	X	
Prior DCCV?	X	
CHA2DS2VASC score	X	
Moderate or Severe Valvular Disease?	X	
Heart Failure with Reduced Ejection Fraction?	X	
Body Mass Index	X	
Date of Birth	X	
Sex	X	
Pregnancy Test	X	
Amiodarone (yes/no)	X	
Flecainide (yes/no)	X	
Beta blockers (yes/no)	X	
ACE Inhibitor or ARB (yes/no)	X	
Randomization	X	
DCCV		X
ECG or Monitor 1 minute after 1 st shock		X
Adverse Event Assessment 10 minutes after shock or at conclusion of procedure		X

1. BACKGROUND

Direct current cardioversion (DCCV) is widely used for restoring normal sinus rhythm (NSR) in patients with atrial fibrillation (AF)^{1,2}. More than 1500 DCCV procedures were performed in the Inova health system in 2022. Identifying the safest and most efficacious method is important. Despite decades of clinical use, the ideal shock waveform and energy for DCCV from AF to NSR are still unknown. Two FDA approved external defibrillation devices (Zoll series R and Lifepak 15/20) are used to deliver DCCV shocks in clinical practice in the Inova Health System. These devices differ in shock waveform and maximum energy delivery. The Zoll Series R device uses a Rectilinear Biphasic Waveform (RBW) with a maximum energy of 200 Joules while the Physiocontrol Lifepak Series 15/20 devices use a Biphasic Truncated Exponential (BTE) Waveform with a maximum energy of 360 Joules. Four small studies (n=50-101 patients per group) have compared the efficacy of RBW and BTE waveforms for DCCV of AF to NSR^{3,4,5,6}. None of the studies were adequately powered to detect clinically meaningful differences in efficacy or safety of the waveforms. All 4 studies used a protocol starting with low energy shocks (50-100J) and escalating the output over multiple shocks. Since these studies have been published, maximum energy shocks were found to be more effective and safer than escalating low-energy shocks for DCCV⁷ and maximum energy first shocks are now recommended in European guidelines⁸. We therefore propose an adequately powered randomized controlled trial (RCT) evaluating the efficacy and safety of maximum energy RBW and BTE shock waveforms delivered by the Zoll series R and Physiocontrol Lifepak Series 15/20 devices respectively.

1.1 Study Disease(s) or Condition(s)

AF is the most common cardiac arrhythmia affecting more than 46 million people worldwide. More than 86,000 patients have been diagnosed with AF in the Inova health system in the past year. AF is frequently associated with symptoms of fatigue, shortness of breath and palpitations. DCCV is a commonly performed procedure to temporarily restore NSR in patients with symptomatic AF or in those with hemodynamically intolerable AF.

1.2 Product(s) / Agent(s)

The Zoll series R defibrillator is an FDA approved device with indications for defibrillation of cardiac arrest where there is an apparent lack of circulation and for synchronized DCCV of certain atrial and ventricular arrhythmias. It is indicated for adult and pediatric patients. The device is connected to the patient through the one-step cable and the manufacturer recommends also connecting a separate ECG cable. The Zoll series R defibrillator has been deployed across the Inova health system and is currently available for clinical use in all clinical areas performing DCCV. For this study the device will be used on label and according to manufacturer recommendations. All shocks will be synchronized and delivered in the manual mode at 200J through the one touch hands-free pads. No shocks will be delivered through paddles. The Physiocontrol Lifepak 15 and 20 monitor/defibrillators are FDA approved devices with indications for termination of certain fatal arrhythmias such as ventricular fibrillation and symptomatic ventricular tachycardia. Delivery of energy in synchronized mode is a method for

A Pragmatic Randomized Clinical Trial Comparing Rectilinear Biphasic Waveform and Biphasic Truncated Exponential Waveform Shocks for Cardioversion of Atrial Fibrillation (Zoll vs Lifepak-RCT) |

PI: [name]

treating AF, atrial flutter, paroxysmal supraventricular tachycardia, and in relatively stable patients with ventricular tachycardia. The Lifepak 15 and 20 defibrillators have been deployed across the Inova health system and are currently available for clinical use in all clinical areas performing DCCV. For this study all shocks will be delivered in the manual mode at 360J synchronized through hands-free pads. No shocks will be delivered through paddles.

1.3 Rationale

Four small studies (n=50-101 patients per group) have compared the efficacy of RBW and BTE waveforms for DCCV of AF to NSR^{3,4,5,6}. None of the studies were adequately powered to detect clinically meaningful differences in efficacy or safety of the waveforms and all used escalating low-energy shocks. Since these studies have been published, maximum fixed energy shocks were found to be more effective than escalating low-energy shocks for DCCV and maximum energy first shocks are now suggested in European guidelines⁸. We therefore propose an adequately powered randomized controlled trial (RCT) evaluating the efficacy and safety of maximum energy RBW and BTE shock waveforms delivered by the Zoll series R and Lifepak 15 and 20 devices respectively.

1.4 Relevant Literature and Data

In 1959 Lown developed a direct current waveform to improve efficacy and reduce adverse events associated with defibrillation performed with alternating current. The monophasic waveform he developed was in use until the 1980s when biphasic waveforms were shown to further improve defibrillation success. Several biphasic waveforms have been developed including the BTE and RBW waveforms. These waveforms have been incorporated into competing FDA approved devices manufactured by Zoll, Phillips, and Physiocontrol/Medtronic.

- The first comparative study of biphasic DCCV shock waveforms was published in 2003³. Investigators randomized 101 patients with AF to DCCV using escalating RBW shocks from a Zoll M series defibrillator (50, 100, 200, 200J) or escalating BTE shocks from a Physiocontrol Lifepak-12 defibrillator (50, 100, 200, 200J). If the fourth shock at 200J failed in either arm a single 360J shock was delivered from the BTE device. Patches were placed in an antero-posterior location. The overall efficacy was 97.9% in the BTE group and 100% in the RBW group (p=0.29). The study was underpowered to detect a clinically significant difference between groups. Enrollment would have allowed the study to detect an efficacy difference of 20% or more.
- The second observational study was published in 2004⁴. Patients with AF underwent DCCV with a series of escalating RBW shocks from a Zoll series M

A Pragmatic Randomized Clinical Trial Comparing Rectilinear Biphasic Waveform and Biphasic Truncated Exponential Waveform Shocks for Cardioversion of Atrial Fibrillation (Zoll vs Lifepak-RCT) |

PI: [name]

defibrillator (50,100,150, 200J) or a BTE shock (50,100,150, 300, 360J) from a Medtronic Physiocontrol Lifepak 12 defibrillator. If DCCV was unsuccessful at the maximum deliverable energy patients were crossed over to the other device. Patches were placed in an antero-posterior location. 145 patients were enrolled but treatment allocation was not randomized because of patient refusal or physician refusal to participate in the study. The success rate was 97% in both groups ($p=1.0$). 2/71 patients in the RBW group failed maximum energy shock (200J) and crossed over to the 360J RBW shock and were successfully converted. 2/71 patients in the BTE group failed maximum energy shock (360J) and crossed over to the RBW group. Both also failed the RBW shock.

- The third comparative study of the RBW and BTE waveforms was published in 2005⁵. The investigators randomized 188 subjects with AF in a 1:1 fashion to receive escalating low energy RBW shocks (50, 75, 100, 120, 150, 200 J) or BTE shocks (50, 70, 100, 125, 150, 200, 300, 360 J). The shock strength was escalated until success or maximum energy was delivered. If maximum energy shock failed, the patient crossed over to the opposite waveform. 47 patients were excluded leaving a total of 141 patients (71 in RBW and 70 with BTE shocks). The authors found a maximum energy success rate of 93% in patients receiving a RBW shock and 97% in patients receiving a BTE shock ($p=0.44$). Unfortunately, the small study sample size would have allowed the authors to detect a minimum difference in success rate of 14% or more, while a clinically relevant efficacy difference of 5% or more was impossible to detect.
- The fourth comparative study of commercially available biphasic waveforms was published in 2013⁶. The investigators randomized 199 patients to receive DCCV using either a RBW from a Zoll series R defibrillator or BTE from a Phillips Heartstart XL defibrillator using 50, 100, 150, 200, 200 J. The shock strength was escalated until success or maximum energy was delivered. 95% of patients in the RBW and 90.9% of patients in the BTE arms successfully converted to NSR ($P=0.838$). Unfortunately, the small study sample size allowed the study to detect differences in efficacy of 20% or more and they did not deliver maximal energy (360J) shocks using the BTE waveform, limiting the clinical applicability of the findings.
- Since the 4 comparative studies were published, a randomized controlled study in 2021 showed anterolateral patch placement improved DCCV success rate compared to anteroposterior placement⁹. Further, a DCCV protocol using fixed maximum energy shocks was found to be more effective than escalating low-energy shocks⁷. No adequately powered studies have compared a first maximum shock efficacy of RBW (200J) to BTE (360J) waveforms incorporating these recommendations and an anterolateral patch location.

Correlative Studies Background

1.4.1 NA

1.5 Compliance Statement

This study will be conducted in full accordance with all applicable Inova Health System's Federalwide Assurance (FWA), Research Policies and Procedures, and all applicable Federal and State laws. These regulations include, but are not limited to 45 CFR 46, 21 CFR Parts 50, 54, 56, 312, 812, and the Good Clinical Practice: Consolidated Guideline approved by the International Conference on Harmonisation (ICH).

The investigators will perform the study in accordance with this protocol, will obtain consent and/or assent (unless waived by the IRB of record), and will report unanticipated problems involving risk to participants or others and potential serious or continuing non-compliance in accordance with the Inova Health System's Office of Research Policies and Procedures and all federal requirements. Collection, recording, and reporting of data will be accurate and will ensure the privacy, health, and welfare of research participants during and after the study.

2. OBJECTIVES

2.1 Primary Objectives

- 2.1.1 To compare the efficacy of a single 200J RBW shock and a single 360J BTE shock
- 2.1.2 To compare the efficacy of one or two consecutive 200J RBW or 360J BTE shocks
- 2.1.3 To measure the efficacy of cross over from RBW to BTE or BTE to RBW after failing 2 consecutive full output shocks with the first waveform

2.2 Secondary Objectives

- 2.2.1 To compare the frequency of adverse events after one or two 200J RBW or 360J BTE shocks. Patients undergoing cross-over will be excluded from this analysis.

3.2 Community Involvement

Not applicable

3.3 Outside of Organization

Not applicable

4. RESOURCES AVAILABLE

4.1 Conducting Research

30-35 unique patients undergo DCCV for AF in the cardiac diagnostic unit or electrophysiology labs at IHVI each week (1560/year). Assuming 50% of these subjects meet eligibility criteria, we expect to be able to complete enrollment of the 560 patients in approximately 6 months.

The PI will dedicate 5% of his time to conducting and completing the research. Both the Zoll series R and Lifepak 15/20 defibrillators, connector cables, and pads are available in the EP labs and the CDU at IHVI, IAH, and ILH hospitals.

4.2 Medical and/or Psychological Resources

Not Applicable

5. INVESTIGATIONAL PLAN

5.1 General Schema of Study Design

5.1.1 Hypothesis

We hypothesize that the maximal output first shock efficacy of RBW and BTE shocks differs by more than 5%.

5.1.2 Phase of the Trial

This is a single center, investigator-initiated, open-label, pragmatic randomized controlled assessment trial.

5.1.3 Study Treatment

Patients with AF will be randomized to receive either a full output synchronized 200J shock using a RBW waveform from a Zoll R series defibrillator or a full output synchronized 360J shock using a BTE waveform from a Lifepak Series 15/20 defibrillator.

A Pragmatic Randomized Clinical Trial Comparing Rectilinear Biphasic Waveform and Biphasic Truncated Exponential Waveform Shocks for Cardioversion of Atrial Fibrillation (Zoll vs Lifepak-RCT) |

PI: [name]

Success will be defined as NSR 1 minute after the shock. Patients who do not have first shock success will have a second full output shock ≥ 1 minute after the first shock.

Patients who do not have success after a second full output shock will be crossed over to the other defibrillator waveform and receive up to 2 full output shocks with a minimum of 1 minute between each shock to ascertain the outcome of the immediately prior shock.

5.2 Product(s) / Agent(s)

5.2.1 Handling, Storage, Accountability, and Preparation

Both the Zoll Series R defibrillator and the Lifepak 15 and 20 defibrillators and the necessary cables and pads are stored in the cardioversion procedure rooms and the Electrophysiology labs in IHVI, IAH, and ILH hospitals.

5.2.1.1 Acquisition and Accountability

Both defibrillators are already available for clinical use in both the cardioversion procedure rooms and Electrophysiology labs in IHVI, IAH, and ILH hospitals.

5.2.1.2 Storage and Stability

Not applicable

5.2.1.3 Preparation

Not applicable

5.3 Allocation to Treatment Groups and Blinding/Randomization

Patients will be randomly allocated to either treatment group in a 1:1 fashion. Randomization will be blocked by treatment location (Electrophysiology labs versus other environments due to the differing pad locations in these two environments). A randomization sequence will be created in the RedCAP file. Randomization envelopes will be created and stored in the pre-procedure electrophysiology holding areas or electrophysiology labs or the DCCV procedure areas. In the envelope will be the case report form with the treatment assignment listed on it. Prior to the DCCV procedure staff will open an envelope to learn the treatment assignment and then use the assigned defibrillator. Patients, staff, and investigators will be unblinded. The clinical staff will complete the CRF. They will attach the rhythm strip or ECG acquired 1 minute after the shock and place it back in the envelope. They will seal the envelope and place it in a secure location to be gathered by the study team.

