Atrial fibrillation (AF) is a major cause of cardiovascular morbidity and mortality, affecting more than 46 million people worldwide.¹ Direct current cardioversion (DCCV) is used to terminate an episode of symptomatic or hemodynamically unstable AF. The success rate for DCCV is 90-95% and is dependent on patient and procedural characteristics including obesity, use of antiarrhythmic drugs, pad placement, type of shock waveform and shock energy. Biphasic defibrillation waveform shocks improve DCCV success rates for AF to normal sinus rhythm (NSR) compared to monophasic shocks. Various biphasic shock waveforms are available: The Rectilinear Biphasic Waveform (RBW) is used by the Zoll series R defibrillator while the Biphasic Truncated Waveform (BTW) is used in the FDA approved Lifepak model 15 and 20 defibrillators. Despite their routine use in clinical practice, no adequately powered prospective head-to-head randomized controlled trials (RCT) have compared the safety or efficacy of the two biphasic waveforms for DCCV of AF to NSR.

The primary objectives for this pragmatic prospective randomized controlled trial are to 1) compare the efficacy of first shock DCCV from AF to NSR using anterolateral pad placement and a full-output 200J RBW synchronized shock from a Zoll series R defibrillator or a full output 360J BTW synchronized shock from a Lifepak 15 or 20 defibrillator; 2) compare the DCCV efficacy of first or second full output shock 3) compare the DCCV efficacy of third or fourth full output shock after treatment group cross over after first failing 2 consecutive full output shocks from the originally assigned treatment group. The secondary objective is to compare the frequency of skin irritation or damage after first or second shock cardioversion from either defibrillator.

Data will be derived from approximately 560 patients arriving to Inova sites of care in AF scheduled to undergo either AF ablation with expected DCCV or elective stand-alone AF DCCV. Patients will be included if they are in AF prior to their procedure and are willing to sign the consent form and comply with the research procedures. Participants will be excluded if they are in a rhythm other than AF on arrival to IHVI, have not been appropriately anticoagulated with warfarin or direct oral anticoagulant, or have known left atrial appendage thrombus prior to their procedure.

ABBREVIATIONS AND DEFINITIONS

Abbreviation	Definition of Terms
DCCV	Direct Current Cardioversion

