Efficacy Evaluations:	
 1. Proportion of patients in NSR by ECG or monitor 1 minute after the first DCCV shock. 2. Proportion of patients in NSR by ECG or monitor 1 minute after the first or second DCCV shock. 3. Proportion of patients in NSR by ECG or monitor 1 minute after a third or fourth crossover treatment assignment shock after failing first and second shock on original treatment assignment.
Safety Evaluations:	
 1. Number of patients with skin redness, pain or discomfort under the shock electrodes (excluding those with cross-over) 2. Number of patients with arrhythmic events (asystole, atrioventricular block, transient bradycardia or ventricular arrhythmia) within 10 minutes of the last DCCV shock 3. Frequency of pacemaker or ICD dysfunction after shock among patients with prior pacemaker or defibrillator implant
Statistical and Analytical Plan:	
Based on the best available literature we expect the first shock DCCV success rate to be 93% in our population. A total sample size of 538 subjects (269 in each group) will be needed to provide 80% power to reject the null hypothesis (a difference of efficacy < 5%). The analysis will be performed on the intention-to-treat population. The proportions will be compared using both risk difference and risk ratio with corresponding 95% CI. Effects of treatment will be estimated by modified

A Pragmatic Randomized Clinical Trial Comparing Rectilinear Biphasic Waveform and Biphasic Truncated Exponential Waveform Shocks for Cardioversion of Atrial Fibrillation (Zoll vs Lifepak-RCT) |

PI: [name]

	Poisson regression using generalized estimating equations. Outcomes will be compared across pre-specified subgroups and testing will be performed for interactions (sex, body mass index, first or > 1 AF episode, AF type, DCCV location).
Data and Safety Monitoring Plan:	The study PI will be responsible for study safety. One interval analysis will be performed after 50% trial enrollment. No DSMB will be assembled.

TABLE OF CONTENTS

STUDY TITLE.....	Error! Bookmark not defined.
SUMMARY OF CHANGES	i
ABSTRACT	ii
ABBREVIATIONS AND DEFINITIONS.....	iii
PROTOCOL SYNOPSIS	iv
TABLE OF CONTENTS	viii
SCHEMA EXAMPLES.....	Error! Bookmark not defined.
1. BACKGROUND.....	2
1.1 Study Disease(s) or Condition(s)	2
1.2 Product(s) / Agent(s)	2
1.3 Rationale	3
1.4 Relevant Literature and Data	3
1.5 Correlative Studies Background	5
1.6 Compliance Statement.....	5

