12.2 Analytics

All analyses will be performed on an intention to treat basis. We calculated the sample size on the basis of the 3 prior randomized studies that compared RBW and BTE shocks for DCCV of AF. In these studies, the mean overall shock success was 90-97% and the first shock success varied from 54%-90% albeit the first shock was delivered at a lower energy than maximum output. We therefore estimate that the mean first shock success rate will be 93%. A clinically meaningful difference in first full output shock efficacy is 5%. A total study sample size of 544 patients (272 in each group) is needed to provide a power of 80% to reject the null hypothesis (a difference in efficacy of < 5%).

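### Randomisation is blocked by treatment location, but the main treatment-effect analysis is not stated to be stratified by or adjusted for location (minor)

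*Combined protocol and SAP*

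**What the plan says.** **Allocation.** Section 5.3 allocates patients 1:1 and adds: "Randomization will be blocked by treatment location (Electrophysiology labs versus other environments due to the differing pad locations in these two environments".

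**Why location could matter.** The Abstract describes cardioversion success as "dependent on patient and procedural characteristics including obesity, use of antiarrhythmic drugs, pad placement, type of shock waveform and shock energy". Section 1.4 reports that "a randomized controlled study in 2021 showed anterolateral patch placement improved DCCV success rate compared to anteroposterior placement".

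**Main analysis.** The synopsis (Statistical and Analytical Plan) says: "The proportions will be compared using both risk difference and risk ratio with corresponding 95% CI". It then estimates treatment effects by modified "Poisson regression using generalized estimating equations". No stratum, covariate or cluster unit is given.

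**Where location does appear.** The same synopsis entry says "testing will be performed for interactions (sex, body mass index, first or > 1 AF episode, AF type, DCCV location", as part of the subgroup plan.

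**Section 12.2.** It says "All analyses will be performed on an intention to treat basis" and gives the sample size. It names no effect model and no adjustment.

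**The concern.** When allocation is restricted within a factor, the usual practice is for the main analysis to use that factor. If the factor predicts outcome, balancing on it removes some chance variation from the treatment comparison, and an analysis that ignores the factor does not credit that removal. Here the factor was chosen because of pad position, which the plan itself regards as prognostic.

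An interaction test does not fill the gap. It asks whether the treatment effect differs between locations, not whether the main estimate is stratified.

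What is at stake is mostly pre-specification. Patients, staff and investigators know the assignments (sections 5.3 and 10.2.2), and the synopsis plans an interval analysis after half of enrolment. Whether to adjust for location should not be left to be settled once results are visible.

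**Working it through.** **1. The plan's own figure.** Inputs: 93% success and a 5-point difference (section 12.2) and 80% power. Two-sided 5% is assumed, to match the 95% intervals. With 93% v 98% and mean rate 0.955:

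n = [1.960 × √(2 × 0.955 × 0.045) + 0.842 × √(0.93 × 0.07 + 0.98 × 0.02)]² / 0.05² = 268.7, so 269 per group and 538 in total.

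This is the synopsis figure. At section 12.2's 272 per group, power is 80.5%. The sample size therefore comes from an unstratified two-proportion comparison, and stratifying the analysis does not alter it.

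**2. Large-sample size of the effect.** Let a and b be the success rates in the two locations (the same in both arms under no difference) and w the share of patients in the first, with m = wa + (1−w)b. The ratio of unstratified to stratified variance is

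m(1−m) / [w·a(1−a) + (1−w)·b(1−b)].

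The documents give neither a, b nor w, so these are assumptions:

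| Location rates | Split | Variance ratio | SE ratio |
|---|---|---|---|
| 92% v 94% | 50:50 | 1.0015 | 1.0008 |
| 91% v 95% | 50:50 | 1.0062 | 1.0031 |
| 90% v 96% | 50:50 | 1.0140 | 1.0070 |
| 88% v 97% | 40:60 | 1.0326 | 1.0162 |
| 87% v 99% | 50:50 | 1.0585 | 1.0289 |

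For example, 90% v 96%: 0.93 × 0.07 = 0.0651; (0.0900 + 0.0384)/2 = 0.0642; 0.0651/0.0642 = 1.0140. In the last row the nominal 5% test has size 2[1 − Φ(1.960 × 1.0289)] = 4.4%.

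**3. Check at the trial's size.** Simulation of the risk difference under no treatment difference: 272 per arm, allocation balanced within location, 1,000,000 replicates, unstratified Wald v Mantel-Haenszel. With balanced allocation the two point estimates are the same number. SD and SE are in percentage points.

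| Location rates | Empirical SD | Mean SE, unstratified | Mean SE, stratified | Rejection, unstratified v stratified |
|---|---|---|---|---|
| 92% v 94% | 2.188 | 2.178 | 2.172 | 5.04% v 5.06% |
| 91% v 95% | 2.182 | 2.178 | 2.167 | 5.02% v 5.09% |
| 90% v 96% | 2.172 | 2.178 | 2.159 | 4.89% v 5.05% |
| 88% v 97% (40:60) | 2.095 | 2.120 | 2.082 | 4.71% v 5.16% |

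A separate run with score-type tests (pooled z v Cochran-Mantel-Haenszel, 400,000 replicates, equal split, 93% average) gave 4.56% v 4.88% at a 10-point gap and 4.46% v 4.99% at a 12-point gap.

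At small gaps the unstratified SE is marginally below the empirical SD; it is above it only at the wider gaps. The stratified SE is slightly low throughout.

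**4. Power and conclusions.** For 90% v 96% and 88% v 97%, with critical values calibrated to 5%, power at 93% v 98% is 83.1% v 83.4% and 83.7% v 83.8% (unstratified v stratified). At 90.5% v 95.5% it is 64.2% v 64.4% and 64.6% v 65.2%. Across the null and these two alternatives, the choice of analysis changes the 5% verdict in 0.2% to 1.5% of trials for the risk difference and in at most 0.5% for the risk ratio.

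**The case against.** The strongest reply is that almost nothing follows from the omission. With no covariates listed, the natural reading of the synopsis is an unadjusted comparison, which is valid here and at worst mildly conservative. Location is not ignored, because subgroup results are pre-specified. The prognostic strength of location is also assumed: no section says which pad positions the electrophysiology labs use, how often, or with what success, and the effect vanishes if location does not predict outcome. All of this stands, and it keeps the point minor. It does not answer the narrower question of why a factor important enough to randomise on is absent from the main estimate.

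Two partial defences are weaker. The generalised estimating equations might be meant to handle location, but no cluster unit is named, and two clusters would not support a reliable robust variance. It might also be said that blocking is not stratifying, but blocking by a two-level location factor does restrict allocation within location.

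A reader might infer more than the documents support:
- *That the unstratified standard error is generally too large.* At 272 per arm it is not when the gap between locations is 2 or 4 points.
- *That stratifying brings the confidence interval into line with the design.* At 90% v 96% the unstratified SE is 0.3% above the empirical SD and the stratified SE 0.6% below it. The change trades slight conservatism for very slight anticonservatism.
- *That the pad wording is contradictory.* Section 9.2 allows other positions where anterolateral placement is impossible, so it can be read consistently with section 5.3 and the Abstract.

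**Conclusion.** The point holds as a minor one. The plan blocks randomisation by a factor that it links to pad position, and so to success, and does not carry that factor into the main treatment-effect analysis.

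Under assumed location gaps of 6 to 12 points, the unstratified risk-difference test is mildly conservative. Below that range the two analyses are practically indistinguishable. A reader might infer a biased estimate, a type I error inflated by leaving location out, or a trial of the wrong size. None of these follows: allocation is 1:1 within location, the error of omission runs towards conservatism, and the sample size is unaffected.

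The size rests on assumed location rates and splits, a two-sided 5% level, 272 evaluable patients per arm and balance within location. That the factor is absent from the stated main analysis rests on the text alone.

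**What to change.** In the synopsis (Statistical and Analytical Plan) and in section 12.2, state that:
- the primary risk difference is the Mantel-Haenszel estimate stratified by the two-level randomisation factor, electrophysiology labs v other environments;
- the risk ratio comes from the modified Poisson model with location as a term;
- the location subgroup and interaction report stays as planned.

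One method should be named for each measure. A location term in a log-link Poisson model gives an adjusted risk ratio, not a stratified risk difference, and offering alternatives would leave open part of the choice that the change is meant to close.

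The cost is a sentence or two in each place. Location is already known from randomisation, so no new data are needed and the sample size does not change. The wording should be settled before any outcome comparison by arm is seen.

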11. DATA AND SPECIMEN COLLECTION AND MANAGEMENT

11.1 Data Collection and Management

Data will be collected by study staff on case report forms. The CRF will be completed by the physician investigator at the conclusion of the procedure. The CRFs will be placed in a sealed envelope and stored in a locked file cabinet in the EP lab or CDU care area. The

PI: [name]

study staff will collect the completed forms weekly. The study staff will not need to be present during enrollment or CRF completion. These forms will be scanned and the associated file stored in REDCAP as source documents. Pre and post DCCV monitoring strips or ECGs to document pre DCCV AF and post DCCV rhythm will be stored in PDF format or printed on paper and scanned as source documents into the CRF.

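### The only recording form described sits in the randomisation envelope and is completed after the procedure, so baseline and subgroup items are recorded once arm and shock result are known

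*Combined protocol and SAP*

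**What the plan says.** Section 5.3 describes the allocation step. On the form it says: "In the envelope will be the case report form with the treatment assignment listed on it". On its use: "Prior to the DCCV procedure staff will open an envelope to learn the treatment assignment and then use the assigned defibrillator". On blinding: "Patients, staff, and investigators will be unblinded". On who fills in the form: "The clinical staff will complete the CRF".

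Section 11.1 gives a time and a different person: "The CRF will be completed by the physician investigator at the conclusion of the procedure". It adds: "The study staff will not need to be present during enrollment or CRF completion".

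The schedule of assessments, placed before section 1, puts the baseline items in the Screening (Pre-Op) column, above the randomisation row. One of them is "Duration of AF Assessment (< 7 days, 7 days-365 days, > 365 days". The others include months since diagnosis, prior DCCV, CHA2DS2VASC, valve disease, heart failure, body mass index, sex and drugs.

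The Synopsis (Statistical and Analytical Plan) plans subgroup analyses in which "testing will be performed for interactions (sex, body mass index, first or > 1 AF episode, AF type, DCCV location".

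**The concern.** A baseline or subgroup variable is safe to use when its recorded value cannot depend on the arm or the outcome. The simplest guarantee is to record it before allocation. Here the form is reached by opening the envelope that reveals the arm, and it is completed after the shock has worked or failed.

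Some items leave room for judgement or recall. An operator who has just seen a failed shock may be readier to call the AF longer-standing. If that tendency differs between devices, it can create or hide a treatment-by-AF-type interaction. The baseline table also becomes a weaker check on allocation, because its entries were made with the arm known.

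**Working it through.** The plan gives no figure on this point. The main check is to set the steps side by side, and the arithmetic then shows how sensitive a subgroup result could be.

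**Order of events**

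| Step | Source | What is known by then |
|---|---|---|
| Chart review and discussion with the patient | 8.1.2, 9.1.5 | Neither arm nor result; no statement that values are written down |
| Baseline items due | Schedule, Screening (Pre-Op) column | Neither arm nor result, if done as scheduled |
| Envelope opened and form reached | 5.3 | Arm |
| Shock given, rhythm read at 1 minute | 5.1.3, 12.1 | Arm and result |
| Form completed | 11.1 | Arm and result |

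Section 11.1.3 refers the reader to the case report form for the data collected. No screening form, eligibility log or pre-allocation REDCap entry is described. Recording after allocation follows from 5.3 alone; recording after the result rests on 11.1.

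**Which subgroups are exposed**

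- Sex and body mass index can be checked against the chart, since 11.1.3 collects the medical record number.
- DCCV location is the randomisation blocking factor (5.3).
- AF type has no row of its own in the schedule. The AF duration class is the nearest item, and it depends on history.
- First versus later AF episode has no row in the schedule. Neither prior DCCV nor months since diagnosis supplies it.

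**Expected first-shock failures**

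Inputs: 93% success and a 5-point difference (12.2). Reading these as 93% v 98%, with an assumed two-sided 5% level, 80% power, pooled variance and no continuity correction:

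n per arm = [1.960 × √(2 × 0.955 × 0.045) + 0.842 × √(0.93 × 0.07 + 0.98 × 0.02)]² / 0.05² = 268.7, so 269.

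This reproduces the Synopsis figure of 269 per arm. Section 12.2 uses 272, which gives 80.5% power. With 272 per arm:

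- 93% v 98%: 272 × 0.07 = 19.0 and 272 × 0.02 = 5.4, about 24 failures in all.
- 93% in both arms: 2 × 19.04 = 38.1, about 38 failures.

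**Sensitivity illustration**

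Assumptions: two subgroup classes of 136 in each arm, 93% success in both arms, and relabelling in one arm only. The starting failure rate is 9.5/136 = 7.0% in each class.

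| Failures relabelled | Class A | Class B | Gap | Interaction p |
|---|---|---|---|---|
| 3 | 6.5/133 = 4.9% | 12.5/139 = 9.0% | 4.1 points | about 0.34 |
| 5 | 4.5/131 = 3.4% | 14.5/141 = 10.3% | 6.8 points | about 0.11 |

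The p-value is a Wald test on the ratio of failure risk ratios, the other arm staying at 7.0% in both classes.

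**If both arms relabel the same fraction (3/19)**

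- At 93% v 98%, the second arm has about 5 failures, 2.5 per class. It relabels 5 × 3/19 = 0.79, giving 1.71/135.21 = 1.3% and 3.29/136.79 = 2.4%, a gap of 1.1 points. The net interaction on the risk-difference scale is 4.1 − 1.1 = 3.0 points.
- With equal true rates, the gaps cancel (4.1 − 4.1 = 0) and no interaction is expected.

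**The case against.** The strongest reply is that the case report form is not among the documents. That it is the only form, and which fields it holds, is inferred from silence. The schedule already places baseline items pre-op, and 8.1.2 has the chart reviewed and the patient seen beforehand. Section 11.1 says when the form is completed, not when baseline is first ascertained. This stands as a limit on certainty: a reader might infer that nothing can be written down before allocation, and the documents do not go that far. It does not remove the point, because the one recording step they do describe comes after allocation and result.

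Other parts of the reply also stand:

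- A reader might infer that the main result is at risk. The intention-to-treat first-shock comparison does not use these variables.
- A reader might take the missing AF-episode row to mean that the item is not collected. The schedule is not exhaustive; it also omits the heart rate and blood pressure required by 9.1.3. The item may be on the unseen form.
- A reader might infer that shredding the paper destroys the audit trail. The forms are scanned into REDCap first (11.1.1, 11.3), and an untimed original would show the order of recording no better than its scan.
- A reader might set a shift of about 4 points against the 5-point difference in 12.2. That threshold concerns the overall first-shock difference, and the 4-point figure needs relabelling in one arm only.

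**Conclusion.** The point holds as a weakness in the stated procedure. Followed as written, 5.3 and 11.1 have baseline items recorded after arm and shock result are known, contrary to the order in the schedule.

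Its reach is narrow: the interaction tests on AF type and AF episode, and the baseline table. With about 24 to 38 first-shock failures expected under the two scenarios, three relabelled failures can open a gap of about 4 points between classes in one arm. The net effect falls to about 3 points, or to none, when both arms relabel alike. These figures rest on an assumed even split and assumed relabelling. They describe sensitivity only; nothing in the documents shows that relabelling will happen. The change is still worth making because it is cheap and closes the route.

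Separately, 5.3 and 11.1 disagree on who completes the form, clinical staff or the physician investigator, and should be reconciled.

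**What to change.** - In 5.3 and 11.1, divide the form. Keep a baseline and eligibility page outside the envelope. It should hold every screening item in the schedule plus first versus later AF episode, and carry the study or envelope number for linkage.
- Require that page to be completed, timed and initialled before the envelope is opened, and stored securely.
- Leave the assignment, shocks, rhythm and adverse events on the page inside the envelope, and limit end-of-procedure completion in 11.1 to that page.
- Add an AF-episode row to the schedule. Substituting prior DCCV for this subgroup would change the question being asked.
- Name one role that completes each page, and use it in both sections.

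The cost is a reprinted form, short edits to 5.3, 11.1 and the schedule, and about a minute of writing before the procedure. No visit or staff is added, since the chart review and discussion already take place beforehand (8.1.2). The downside is one more page to link and store securely, which matters because 13.1.2 names loss of PHI as the only risk of participation.
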